**Table 1-2 Analysis by treatment group**

| Endpoint/analysis  | AIN457 150 mg FI
AIN457 150 mg FI switch to 300mg FI
AIN457 300 mg FI
AIN457 150 mg SoR
AIN457 150 mg SoR switch 300 mg FI
AIN457 300 mg SoR
AIN457 300 mg SoR switch 300 mg FI
AIN457 300mg OL | AIN457 150mg FI(NSW+SW) | Any AIN457 150mg
Any AIN457 300mg | Any AIN457 |
|--|--|-------------------------|--------------------------------------|------------|
| Subject disposition  | X  |                         |                                      | X          |
| Demography & baseline characteristics                        | X  |                         |                                      | X          |
| Previous & concomitant medication                            | X  |                         |                                      | X          |
| Medical history  | X  |                         |                                      | X          |
| Study medication: duration of exposure                       | X  |                         | X                                    | X          |
| Maintanance of PASI 75 response                              | X  |                         |                                      |            |
| PASI 50/75/90/100 and IGA mod 2011 0 or 1 response over time | X  | X                       |                                      |            |
| PASI score over time   | X  | X                       |                                      |            |
| IGA mod 2011 score over time                                 | X  | X                       |                                      |            |
| Relapse  | X  |                         |                                      |            |
| Rebound  | X  |                         |                                      |            |
| DLQI 0 or 1 achievement                                      | X  | X                       |                                      |            |

|                          |  |                         |                                      |            |
|--------------------------|--|-------------------------|--------------------------------------|------------|
| Endpoint/analysis | AIN457 150 mg FI
AIN457 150 mg FI switch to 300mg FI
AIN457 300 mg FI
AIN457 150 mg SoR
AIN457 150 mg SoR switch 300 mg FI
AIN457 300 mg SoR
AIN457 300 mg SoR switch 300 mg FI
AIN457 300mg OL | AIN457 150mg FI(NSW+SW) | Any AIN457 150mg
Any AIN457 300mg | Any AIN457 |
| DLQI                     | X  |                         |                                      |            |
| EQ-5D                    | X  |                         |                                      |            |
| HAQ©-DI                  | X  | X                       |                                      |            |
| Safety analysis          | X  |                         | X                                    | X          |

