Subjects from the CAIN457A2304 maintenance period will continue the treatment regimen and dose that they were assigned to (Fixed interval regimen or Retreatment at start of relapse regimen) during the maintenance treatment period of the core study and return for visits every four weeks up until Week 156. Subjects and study personnel will remain blinded during the first two years of the treatment period (except for patients in the open label part of the study). The last blinded dose of the treatment period is administered at Week 152.

At Week 156, subjects will be unblinded and will have the option (based on investigator judgment) to switch dosing regimens, with the specific options depending on the blinded treatment assigned until that point. Generally, subjects may switch off of the SoR treatment regimen to active secukinumab treatment every four weeks, and subjects may switch from secukinumab 150 mg s.c. to secukinumab 300 mg s.c. After Week 156, office visits will only be required every 12-16 weeks until Week 260 (End of Treatment period for CAIN457A2304E1) unless a subject continues with the SoR treatment regimen. Specific details of the open-label treatment options for unblinded subjects starting at Week 156 are described in Section 5.2 and in Table 5-1.

Subjects from the CAIN457A2307 maintenance period will continue in the treatment regimen and dose that they received during the CAIN457A2307 maintenance treatment period (i.e., 300 mg sc secukinumab every four weeks), and return for visits every four weeks up until Week 156. After Week 156, subjects will continue being treated every four weeks, but will only be required to come in for office visits every 12-16 weeks. These subjects were treated open-label during the core study, and will continue to be treated open-label during the treatment period of CAIN457A2304E1. The last dose of secukinumab is provided at Week 256, four weeks prior to the end of the treatment period.

Please refer to [Section 5.2](#) for a more detailed description of the treatment arms.

Subjects who discontinue study treatment prematurely during the treatment period should have all Week 260 protocol assessments (EOT) performed approximately four weeks after their last dose of secukinumab/secukinumab placebo and then enter the treatment-free follow-up periods (follow-up period and follow-up 2 period).

Follow-up period (for all subjects)

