3.3 Rationale of dose/regimen, route of administration and duration of treatment

The doses and regimens selected for the secukinumab phase III program were based on phase II trial data. As of the trial initiation, there has not been any data to date to indicate that the doses used in the core studies should be modified. Therefore, this extension study will continue treatment with secukinumab s.c. doses of 150 mg and 300 mg administered every four weeks, and/or at start of relapse (following the randomization that was done during the core studies) for an additional 208 weeks. This will provide long-term secukinumab efficacy and safety data pertaining to the treatment of subjects suffering from chronic plaque-type psoriasis for up to a total of 5 years when combined with the core studies data.

The pivotal phase III trials were analyzed while this extension trial was ongoing and results of protocol CAIN457A2304 showed that the re-treatment at start of relapse maintenance regimen (SoR) was not non-inferior to a fixed interval regimen (FI) with treatment every four weeks and subjects experience better efficacy with 300 mg secukinumab s.c. every four weeks compared to 150 mg secukinumab s.c. every four weeks with similar safety profile between the two doses. Therefore, at Week 156 all patients treated with the SoR treatment regimen are given the option to switch to treatment with active secukinumab every four weeks, and patients treated with secukinumab 150 mg s.c. are given the option to switch to treatment with secukinumab 300 mg s.c. Any switches in treatment regimen or dose are to be made according to the investigator's judgment as the investigator will have three years of experience with the subject and the subject's individual response to secukinumab.

The switch from the lyophilisate to the more convenient prefilled syringe (PFS) is supported by the results of the clinical study CAIN457A2106, which has shown that the exposure and safety profiles of both formulations are highly comparable.

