### 1.1 Statistical and analytical plans

The planned analysis is described in [Section 9](#) (Data Analysis) of the study protocol which is available in [Appendix 16.1.1 of the CSR](#).

This document covers the statistical and analytical plans for the final analysis. All data collected up to end of the study will be analyzed as part of final analysis.

The primary objective of the study is to assess long-term safety and tolerability of secukinumab in subjects with moderate to severe chronic plaque-type psoriasis who completed treatment in the core studies CAIN457A2304 and CAIN457A2307.

The secondary objectives are:

- To evaluate the long-term efficacy of 150 mg and 300 mg of secukinumab administered at the start of relapse versus fixed interval regimens of 150 mg and 300 mg of secukinumab respectively, in subjects with moderate to severe chronic plaque-type psoriasis who are PASI 75 responders at Week 12, with respect to PASI 75 response:
  - at Weeks 104 and 156, for subjects in the fixed interval regimens, or
  - at Weeks 92 and 144, for subjects in the retreatment at start of relapse regimen who do not require active treatment at Week 92 or 144, respectively, or
  - at Weeks 104 and 156, for subjects in the retreatment at start of relapse regimen who do require active treatment at Week 92 or 144, respectively.
- To evaluate the efficacy of secukinumab treatment regimens in subjects with moderate to severe chronic plaque-type psoriasis with respect to PASI 50/75/90/100 and IGA mod 2011 0 or 1 response over time.
- To evaluate the effects of treatment regimens with secukinumab in subjects with moderate to severe chronic plaque type psoriasis with respect to PASI score and IGA mod 2011 score over time
- To assess the effects of secukinumab treatment regimens with respect to EQ-5D score over time
- To investigate the effects of treatment regimens with secukinumab in subjects with moderate to severe chronic plaque-type psoriasis with respect to changes in DLQI over time
- To investigate the effects of treatment regimens with secukinumab in subjects with moderate to severe chronic plaque-type psoriasis with respect to DLQI 0 or 1 achievement over time
- To investigate the potential development of immunogenicity against secukinumab

- To investigate the occurrence of relapses (achieved maximal PASI improvement from baseline in core study is reduced by >50%) and rebounds in subjects on secukinumab therapy

The exploratory objectives are:

- [REDACTED]

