**Retreatment at start of relapse regimen – “SOR”: “start of relapse” either 150 or 300 mg s.c. secukinumab:** “Start of relapse” will be defined as a loss of  $\geq 20\%$  of the maximum PASI gain achieved during the study compared to baseline, *and* a loss of PASI 75 response. Whenever a subject fulfills the start of relapse criteria, active secukinumab will be administered at their scheduled visits (i.e. every four weeks) until the subject is back to PASI 75 response. The dose administered in the maintenance period (secukinumab 150 mg or 300 mg) will be identical to the dose that these subjects received during the induction period. If a subject does not fulfill the criteria of a start of relapse or is back to PASI 75 response after a start of relapse, they will receive placebo injections (two injections per dose) to maintain the blind. This treatment regimen is applied every four weeks, from week 12 up to and including week 48.

**Open label (OL) 300 mg s.c. secukinumab:** All the partial responders at week 12 in induction period in A2304 will enter A2307 double blind i.v. period (for 8 weeks) and these subjects will be randomized with 1:1 ratio into either “300 mg s.c. secukinumab” or “10 mg per kg i.v. secukinumab”. All the subjects will enter open label 300 mg s.c. secukinumab maintenance period from week 8 to week 40.

All the subjects who are eligible from the above 5 treatment groups (4 treatment groups from A2304 and 1 treatment group from A2307) enter the A2304E1 extension study treatment period and continue with same treatment groups. At Week 156, patients under AIN457 150mg FI arm, AIN457 150mg SOR arm, and AIN457 300mg SOR arm could be switched to AIN457 300mg FI arm as determined by physician’s judgement.

For the final analysis, data will be presented for the following treatment groups:

- AIN457 150 mg FI
- AIN457 150 mg FI switch to AIN457 300mg FI
- AIN457 150 mg FI combined non-switch and switch
- AIN457 300 mg FI
- AIN457 150 mg SoR non-switched
- AIN457 150mg SoR switch to AIN457 300mg FI
- AIN457 300 mg SoR non-switched
- AIN457 300mg SoR switch to AIN457 300mg FI
- AIN457 300 mg OL
- Any AIN457 300mg
- Any AIN457 150mg
- Any AIN457

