### **1.5.2 Background and demographic characteristics**

The following common background and demographic variables from **core** study will be analyzed for assessing the baseline comparability:

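### SAP Table 1-2 groups maintenance of response by the later Week-156 switch, which is not reconciled with the FAS rule and leaves neither start-of-relapse arm with a whole-arm column

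*SAP*

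**What the plan says.** The first secondary objective (SAP 1.1) evaluates "secukinumab administered at the start of relapse versus fixed interval regimens of 150 mg and 300 mg of secukinumab respectively", among Week-12 PASI 75 responders. SAP 1.2 records that these responders were re-randomised 1:1 to FI or SoR within dose.

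Maintenance of response serves that objective, and SAP 1.8.1 calls it the main secondary efficacy analysis. It is PASI 75 at Weeks 104 and 156 for FI. For SoR it is PASI 75 at Weeks 92 and 144, or at Weeks 104 and 156 if active treatment was required at Week 92 or 144.

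At Week 156 subjects from the A2304 core study are unblinded and "will have the option (based on investigator judgment) to switch dosing regimens" (Protocol 3.1). Protocol 3.3 explains that "the investigator will have three years of experience with the subject and the subject's individual response to secukinumab".

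The final-analysis group list in SAP 1.2 names the two SoR groups as non-switched and lists their switchers separately. The only group that rejoins switchers and non-switchers of one arm is "AIN457 150 mg FI combined non-switch and switch". In Table 1-2 the row "Maintanance of PASI 75 response" is marked under the block of individual groups only.

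The FAS definition in SAP 1.2 analyses subjects by the treatment assigned at randomisation and, from Week 156, by the treatment to which they were reassigned. SAP 1.8.1 bases the secondary efficacy analyses on the FAS.

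**The concern.** An endpoint that ends at Week 144 or 156 is laid out by a label fixed at Week 156. The person who fixes that label knows the subject's course so far and has just been unblinded. If the choice is related to response, the non-switched and switched columns of a SoR arm are each selected on something close to the outcome, and neither column estimates the arm.

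The comparison at stake is the one that re-randomisation supports: SoR against FI at the same dose. The 300 mg FI group is never split, so 300 mg SoR non-switched next to 300 mg FI would not be like for like. Two programmers could follow the SAP and produce different tables, one by the FAS rule and one by Table 1-2.

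Multiple imputation (MI) has the same exposure. SAP 2.2.2 uses one input record per subject and runs separately by treatment group. If those groups are the Table 1-2 groups, pre-switch visits are imputed conditionally on a later decision.

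**Working it through.** **Order of events.** The last blinded dose is at Week 152 and the switch is at Week 156 (Protocol 3.1). Efficacy is assessed before dosing (Protocol 6.4), and PASI is entered before the IRT is contacted (Protocol 6, order of assessments). The Week-156 PASI therefore precedes any switched dose. Week 144 is 12 weeks before the switch, Week 104 is 52 weeks before and Week 92 is 64 weeks before. No endpoint visit is affected by switched treatment, so the assigned arm is the treatment that applies at all of them.

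**The two rules compared.**
- FAS rule: assigned arm, then reassigned treatment from Week 156. For this endpoint that gives four arms: 150 FI, 300 FI, 150 SoR and 300 SoR.
- Group list and Table 1-2: 150 FI, 150 SoR and 300 SoR are each divided by switch status; 300 FI and 300 mg open label (OL) are not. Neither SoR arm has a pooled column in any row.

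**Which reading the table favours.** The row "Demography & baseline characteristics" sits under the same split header, and SAP 1.5.2 says these core-study variables "will be analyzed for assessing the baseline comparability". Data from before any switch are thus tabulated under one fixed label per subject. The one-record MI input also gives each subject a single group for all visits. Against this, the visit windows in Table 1-8 separate the groups only after Week 156, and AE exposure time is censored at the switch (SAP 1.9.1). Both fit a grouping that changes over time.

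**Illustration of size.** The documents give no switch rates, so every switch probability here is assumed. Let p be the true arm rate, and s1 and s0 the switch probabilities in Week-156 responders and non-responders.

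Non-switched rate = p(1−s1) / [p(1−s1) + (1−p)(1−s0)]

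Switched rate = p·s1 / [p·s1 + (1−p)·s0]

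With p = 0.60, s1 = 0.40 and s0 = 0.60:
- non-switched: 0.36 / (0.36 + 0.16) = 0.692
- switched: 0.24 / (0.24 + 0.24) = 0.500

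| p | s1 | s0 | Non-switched | Switched |
|---|---|---|---|---|
| 0.60 | 0.50 | 0.50 | 60% | 60% |
| 0.60 | 0.40 | 0.60 | 69% | 50% |
| 0.60 | 0.30 | 0.70 | 78% | 39% |
| 0.60 | 0.85 | 0.95 | 82% | 57% |
| 0.50 | 0.40 | 0.60 | 60% | 40% |
| 0.80 | 0.40 | 0.60 | 86% | 73% |

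In the fourth row 0.60 × 0.85 + 0.40 × 0.95 = 89% of the arm switches, so the switched column is close to the whole arm. The signs reverse if responders switch more often.

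**Scale.** Protocol 9.7 plans about 148 per arm, which reproduces: 918 × 0.95 × 0.85 × 0.80 / 4 = 148.3. At 60% of 148, the planned score interval with continuity correction runs from 52% to 68%. The 40%/60% case moves the columns 9 points up and 10 points down, slightly more than that interval's half-width of about 8 points.

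**The case against.** A reader might infer that the SAP nowhere says assigned arms apply up to Week 156. It does: the FAS definition says so and governs secondary efficacy. The defect is that this rule is not carried into Table 1-2, and its wording does not settle the Week-156 visit itself. Nor is it right that subjects who left before Week 156 have no place. Under the FAS rule, a subject who was never reassigned stays in the assigned arm.

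A reader might also infer an undisclosed departure from the protocol. Protocol 9 already lists an open-label switch group. SAP 1.1.1 announces that non-responder imputation is dropped for this endpoint. The rule counting switchers as non-responders sits in the same Protocol section (9.4.3), so it can reasonably be read as covered.

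Table 1-2 is a coarse grid. One mark serves eight groups, including 300 mg OL, whose subjects come from the Week-12 partial responders (SAP 1.2: "All the partial responders at week 12 in induction period in A2304 will enter A2307") and fall outside this objective. The mark does not prove that a separate estimate is planned for each group. The MI code is a generic template, and MI is secondary to the as-observed analysis.

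There is real mitigation. The next row of Table 1-2 marks the pooled 150 mg FI column for PASI response over time, so whole-arm 150 mg FI PASI 75 rates at Weeks 104 and 156 are planned. As-observed SoR counts can be summed by hand; MI intervals could only be approximated from the separate groups. No formal testing is planned (SAP 1.8.3).

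These points narrow the concern to the two SoR arms and the MI step. They do not remove it, because the listed groups and the FAS rule still give different tables.

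**Conclusion.** The point holds as an unreconciled conflict within the SAP that should be fixed. Followed as listed, Table 1-2 selects the SoR columns on an unblinded choice made at or after the endpoint visits, and omits the re-randomised SoR versus FI display that the first secondary objective calls for. Followed by the FAS rule, it does not.

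The documents do not support a claim that the results are biased by a known amount or in a known direction. The distortion is zero if switching is unrelated to response. The 69%/50% figures rest on assumed switch rates tied to Week-156 response. They do not transfer directly to SoR subjects scored at Week 144, or to the Week 92/104 time point. No alpha or power is affected. Whether the three-year interim analysis listed in SAP 1.12 tabulated the four arms cannot be seen from these documents.

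**What to change.** In SAP 1.2 and Table 1-2, state that maintenance of response, and the SoR efficacy summaries up to and including Week 156, are tabulated by the four arms assigned at the Week-12 re-randomisation (150 FI, 300 FI, 150 SoR, 300 SoR), with switchers and non-switchers pooled. Define the MI treatment group for those visits as the same four arms. Keep the switch/non-switch split for visits after Week 156.

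The cost is a few table columns and one MI rerun, with no new data. A descriptive within-dose SoR minus FI difference with a 95% confidence interval could be added, but it is optional and not part of the correction.

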### **1.3 Subgroup definitions**

No subgroup analysis will be presented in the final analysis. HAQ-DI will be analyzed only for subjects with PsA at Core study entry

### **1.4 Assessment windows, baseline and post baseline definitions, missing data handling**

#### **1.4.1 Assessment windows**

No assessment windows have been defined for this study. Visit windows are described below.

If not otherwise specified, ‘first dose’, ‘randomization’ and ‘baseline’ are with respect to core study.

#### **1.4.2 Study Day 1 and other study days**

The first day of administration of randomized study treatment (first dose) is defined as *Study Day 1 or Day 1*.

All other study days will be labeled relative to Day 1. For event dates on or after Day 1, study day for a particular event date is calculated as [Date of event] – [Date of first dose]+1, i.e., Day 2, Day 3, etc., will be one day, two days, etc., after Day 1, respectively. For the dates before Day 1, study day for an event date is calculated as [Date of event] – [Date of first dose], i.e., Day -1, Day -2, etc., will be one day, two days, etc., before Day 1, respectively. Duration of an event will be calculated as (Event end date – Event start date + 1).

The descriptor “Day 0” will not be used.

#### **Missing data**

For laboratory test values below Lower Level of Quantification (LLQ) or above Upper Level of Quantification (ULQ) will be imputed as LLQ or ULQ value, respectively. The numerical part of the reported result will be treated as the actual LLQ or ULQ. These laboratory values will be displayed in listings using the standard unit with the reported sign (“<” or “>”).

#### **1.4.3 Screening (core and extension), baseline and post-baseline definitions**

*Screening* refers to any procedures (e.g., checking inclusion and exclusion criteria) performed prior to the date of first dose of study treatment in core study A2304 (for safety analysis) or prior to the first randomization date (for efficacy analysis) in A2304. Of note, re-randomization will not be used for baseline definition and only one baseline value will be defined referring to the first randomization.

*Screening2* refers to any procedures (e.g., checking inclusion and exclusion criteria) performed prior to the date of first dose of study treatment **in extension** study A2304E1 (for safety analysis and efficacy analysis).

Per protocol, subject informed consent must be obtained prior to performing any study related activity. The date of signing informed consent is the start date of screening period. Any assessment obtained during the screening period will be labeled screening assessment. Assessments made on Day 1 may occur before or after the randomization or the first dose. Further information will be found in [\[PDS\]](#).

For efficacy analyses, baseline is the last assessment (including unscheduled visits) obtained before the first randomization in the core study A2304. All assessments obtained after randomization are considered as post-baseline unless otherwise specified.

For safety analyses, baseline is the last assessment (including unscheduled visits) obtained before the first dose of study treatment. All assessments obtained after the first dose of study drug are considered as post-baseline unless otherwise specified.

In general, a baseline value refers to the last measurement made prior to administration of the first dose of study treatment. However, for PROs (e.g. patient's assessment of PsA pain), lab, ECG if no pre-treatment value exists, also a value recorded after first dose can be used as baseline if it was collected on the same day as first dose.

